Table 4 summarizes the incidence of fibrosis and retraction (grade 1-3) among 276 patients treated in our current protocol of Image guided Radiotherapy for PBI, using five consecutive fractions of 6Gy. While the degree of this complication also reflects the different surgical techniques of segmental mastectomy, it appears that approximately 1/3 patients suffer some degree of breast distortion/fibrosis with the current hypo-fractionated regimen of 6GyX5. The current trial is designed as a non-inferiority study, powered to enable the detection of 10% or more difference in the incidence of fibrosis.

(276 women treated with prone partial breast radiotherapy 6 Gy x 5)				
`	Fibros		Retract Atrop	ion/
Grade	Number of patients	Percent	Number of patients	Percent
1	68	24.64	63	22.83
2	18	6.52	21	7.61
3	3	1.09	4	1.45
Total Patients with Grades 1-3	89	32.25	88	31.89
Total Number of Patients in Study	276		276	

Table 4 INCIDENCE OF FIRROSIS AND RETRACTION

Recently, Quarmby et al. reported on TGFbeta1 gene polymorphisms on DNA obtained from 103 breast cancer patients who received radiotherapy. Patients who are carriers of specific polymorphisms of TGF-beta -509TT or +869CC alleles were between 7 and 15 times more likely to develop severe fibrosis. [18]

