13.0 STATISTICAL AND DATA MANAGEMENT CONSIDERATIONS

Study Design: This study is a prospective randomized controlled trial to test the hypothesis that 8 Gy x 3 fractions is not worse that 6 Gy X 5 fractions, with respect to the development of breast fibrosis.

The current 6X5 schedule results in 1% 5 year recurrence rate and 10% of grade 2 or 3 fibrosis and approximately 32% of any induration or retraction, measured at after a minimum of 6 months from treatment. In other words approximately one out of 10 patients experience grade 2-3 fibrosis after lumpectomy and partial breast radiation.

Based on our prior experience, we observed a 10% rate of grade 2-3 fibrosis in these patients. With 142 patients randomized to each of the two treatment arms, we can test the hypothesis that the rate of fibrosis with 8Gy x3 is not more than 10% worse than the expected rate on the 6 Gy x 5 arm with one sided alpha =0.025 and power =80%. The trial will have a planned interim analysis when 142 patients across both arms are evaluable for fibrosis assessment at 2 years from accrual. Table 7 below provides the stopping boundaries for the interim analysis.

All analyses may be stratified by whether a ppatient started treatment within 60 days from surgery or within 90 days from surgery.

 Table 7 Stopping Boundaries for Non-inferiority with Respect to Proportion of Patients with

 Fibrosis Treated with 8Gy x3 Compared with Control of 6GY x5 Overall 1-sided alpha = 0.025,

 power =80%, O'Brien-Fleming Boundaries Calculations from EAST V 6.2, Cytel Inc.

 To Deject Us of Non-inferiority

		To Reject Ho of Non-inferiority				
Analysis	Number of Patients Randomized and Evaluable for Fibrosis	Critical Value of z-statistic	Alpha level	Difference in Proportion of Patients with Fibrosis (8Gy x3 -6Gyx5)		
Interim	142	≤-2.96	≤0.0015	≤-0.0493		
Final	284	≤-1.97	≤0.0245	≤0.0299		

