Data management will be carried out by staff of the Department of Radiation Oncology and the NYUCI under the direction of Drs. [name] and [name]. Randomization will occur via REDCap (Research Electronic Data Capture), after consent is acquired, by the PI, research nurse, in the department of Radiation oncology. Data will be entered into Velos, a database management system maintained by the NYULMC PCC CTO according to the procedures of the NYULMC PCC CTO. Patients will be followed every 12 months to evaluate their status with respect to recurrence. Recurrences will be evaluated using standard criteria in the Dept. of Radiation Oncology that are provided in the protocol. Data will be transferred from the Velos database to the Division of Biostatistics for analysis. The Principal Investigator, Research Nurse, and Research Coordinators have access to data collected.

Analysis: Patient characteristics at randomization will be summarized by treatment group using descriptive statistics and graphical displays. For the primary endpoint of fibrosis, the proportions of patients by grade of fibrosis will be compared in the two treatment arms using contingency table methods and chi square tests. The primary analysis will be the difference in proportions of patients with grade 2 or 3 fibrosis between the two treatment groups compared using a non inferiority z- test. Secondary endpoints including rates of recurrence at 1, 2, and 3 years post randomization will be estimated with 95% confidence limits within treatment groups along with plots of Kaplan-Meier time to recurrence curves.

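### Can Table 7's z boundary and difference boundary lead to opposite non-inferiority decisions?

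*Combined protocol and SAP*

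**What the plan says.** Section 13.0 sets the design at "one sided alpha =0.025 and power =80"%, with 142 patients per arm, a margin of 10 percentage points and a planning rate taken from earlier patients: "we observed a 10% rate of grade 2-3 fibrosis in these patients". One interim look is planned: "The trial will have a planned interim analysis when 142 patients across both arms are evaluable for fibrosis assessment at 2 years from accrual". The text then states: "Table 7 below provides the stopping boundaries for the interim analysis".

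Table 7 carries an O'Brien-Fleming caption and cites EAST. Under a single heading for rejecting the null hypothesis it prints three columns, each with a less-than-or-equal sign:

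| Look | Evaluable | z | Alpha | Difference |
|---|---|---|---|---|
| Interim | 142 | -2.96 | 0.0015 | -0.0493 |
| Final | 284 | -1.97 | 0.0245 | 0.0299 |

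The z column is headed "Critical Value of z-statistic"; the last is headed "Difference in Proportion of Patients with Fibrosis (8Gy x3 -6Gyx5"). The Analysis paragraph of the same section describes the primary analysis as the "difference in proportions of patients with grade 2 or 3 fibrosis between the two treatment groups compared using a non inferiority z- test". It does not give the standard error, and no sentence says how the difference column relates to the z column.

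**The concern.** The alpha column is only the tail area of z and cannot conflict with it. The difference column can. It fixes the variance at the planning value, so with equal arms it asks for at least 4 fewer events on 8 Gy x 3 at the interim and allows at most 4 more at the final look, whatever the overall event rate. The z rule moves with the event rate.

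A reader who compares the observed difference with the printed cut-off could therefore stop the trial, or claim non-inferiority, where z would not, or the reverse. The observed rate may well depart from 10%: section 2.7 says "Table 4 summarizes the incidence of fibrosis and retraction (grade 1-3) among 276 patients treated in our current protocol", and that table shows 18 + 3 = 21 patients with grade 2 or 3 fibrosis, or 21/276 = 7.6%. At stake would be the one-sided error rate and the interim stopping decision.

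**Working it through.** **Inputs.** From section 13.0: margin 0.10, planning rate 0.10, one-sided alpha 0.025, power 80%, 142 per arm, interim at 142 evaluable in total. From Table 4: 7.6% as an alternative control rate. Assumptions: equal arms (71, then 142 evaluable per arm), no dropout, an unstratified test.

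**1. Reproduce the plan's figures.**
- Sample size per arm: (1.960 + 0.842)² × 2 × 0.10 × 0.90 / 0.10² = 141.3, rounded up to 142.
- Lan-DeMets O'Brien-Fleming spending at half the information gives z = -2.963 (alpha 0.0015) and -1.969 (alpha 0.0245).
- Difference = 0.10 + z × sqrt(0.18/n). Interim: 0.10 - 2.963 × 0.0504 = -0.0492. Final: 0.10 - 1.969 × 0.0356 = 0.0299.

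The printed values are -0.0493 and 0.0299. The gap of 0.0001 at the interim has no effect, because the observable differences move in steps of 1/71 = 0.0141. Table 7 is not miscalculated.

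**2. Can the columns disagree?** Take z = (difference - 0.10)/SE, with the SE either unpooled or restricted to the null (Farrington-Manning).

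| Look | 6 Gy x 5 | 8 Gy x 3 | Difference | Column | z unpooled | z restricted | z rule |
|---|---|---|---|---|---|---|---|
| Interim | 11/71 | 7/71 | -0.0563 | met | -2.81 | -2.64 | not met |
| Interim | 5/71 | 2/71 | -0.0423 | not met | -3.93 | -3.05 | met |
| Final | 14/142 | 18/142 | 0.0282 | met | -1.92 | -1.85 | not met |
| Final | 6/142 | 11/142 | 0.0352 | not met | -2.31 | -2.06 | met |

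For the first row, unpooled: SE = sqrt((0.0986 × 0.9014 + 0.1549 × 0.8451)/71) = 0.0556, so z = (-0.0563 - 0.10)/0.0556 = -2.81. Conflicts occur in both directions at both looks.

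**3. Size of the effect.** Exact two-look binomial enumeration, stopping if the interim boundary is crossed:

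| Quantity | Column | z unpooled | z restricted |
|---|---|---|---|
| Type I error, 10% v 20% | 5.3% | 2.8% | 2.4% |
| Type I error, 7.6% v 17.6% | 4.0% | 3.0% | 2.4% |
| Power, 10% in both arms | 81.5% | 80.8% | 77.4% |
| Interim crossing, 10% in both arms | 16.2% | 18.4% | 10.1% |
| Different trial conclusion from column, 10% in both arms | - | 3.0% | 4.5% |
| Different trial conclusion from column, 7.6% in both arms | - | 4.6% | 2.5% |

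At the interim alone, the error of the column would be 0.56% (10% v 20%) or 0.29% (7.6% v 17.6%), against the 0.15% printed on that row.

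**4. Which column is the rule?** The primary analysis is a z-test. The only entry in Table 7 that a z-statistic can be compared with is the z column, and it alone is called a critical value. The difference column is z restated on the risk-difference scale at the planning variance. Read this way the passages agree, and the trial's error is the 2.4% to 3.0% in the middle of the table.

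**The case for a change.** The strongest opposing case is that the plan calls the whole table its stopping boundaries, gives the difference its own inequality sign under the rejection heading, and describes the primary analysis as a difference in proportions. Someone who checks the observed difference against 0.0299 is following the table as printed, and that would roughly double the one-sided error at 10% v 20%. Disagreement also grows away from the planning rate. With both arms at 15%, the column and unpooled z reach different trial conclusions in 11.8% of trials. At the interim alone they disagree in 7.6% of trials with both arms at 10% and in 16.6% at 7.6%.

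It can also be said that accepting z does not finish the rule, because the SE is unnamed. With both arms at 10%, the chance of crossing -2.96 at the interim is 18.4% with the unpooled form and 10.1% with the restricted form. Section 13.0 also allows analyses to be stratified by time from surgery, which would alter z again.

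Part of this stands. The difference column is unlabelled, and the SE is not given. But the doubling of error needs a reader to set aside the test the protocol names. The SE is a separate point, which would remain if the difference column were deleted. It is a trade-off between two standard forms: unpooled holds power at 80.8% with error of 2.8% at 10% v 20%; restricted holds error at 2.4% with power of 77.4%. Either is defensible, and a trial statistician fixes the choice, and the use of strata, when preparing the interim look.

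**Conclusion.** The concern is arithmetically right but calls for no change. Table 7's difference cut-offs are the z boundaries correctly converted at 10% in each arm. The Analysis paragraph makes the z-test the primary analysis, so z (at or below -2.96, then -1.97) is the natural rule. Under it the exact two-look one-sided error is 2.4% to 3.0% at control rates of 10% and 7.6%, close to the nominal 2.5%. At a lower control rate (5% v 15%) the unpooled form rises to about 3.3% and the restricted form stays near 2.3%.

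The 5.3% and 4.0% errors belong to a rule the plan does not name. Marking the difference column as approximate would make the table easier to read, but it would alter no result under the plan's own test. These figures rest on 71 and then 142 evaluable patients per arm, no dropout and an unstratified test. The plan fixes the interim only at 142 across both arms, so the counts of 4 fewer and 4 more events would shift if the arms were uneven.

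### Does the by-grade fibrosis comparison need a named effect estimate and confidence interval before its result can be read?

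*Combined protocol and SAP*

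**What the plan says.** The Analysis paragraph of section 13.0 deals with fibrosis in two steps. First, "the proportions of patients by grade of fibrosis will be compared in the two treatment arms using contingency table methods and chi square tests". Second, "The primary analysis will be the difference in proportions of patients with grade 2 or 3 fibrosis between the two treatment groups"; the test applied to that difference is a z-test for non-inferiority. The paragraph then turns to secondary endpoints, for which "rates of recurrence at 1, 2, and 3 years post randomization will be estimated with 95% confidence limits within treatment groups".

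The Study Design text of section 13.0 gives the background rates on 6 Gy x 5: 10% for grade 2 or 3 fibrosis and "approximately 32% of any induration or retraction". Table 4 in section 2.7 gives the fibrosis counts among 276 patients: 68 at grade 1, 18 at grade 2 and 3 at grade 3. Its row "Total Patients with Grades 1-3" shows 89, or 32.25%.

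Section 2.7 also explains the choice of grades. Some induration at the operated site is expected from healing, whereas change beyond grade 1 is taken as a probable late radiation effect.

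**The concern.** The by-grade sentence names tests only. A chi-square test over four grades gives a p-value with no direction and no precision, and that p-value stays the same if the arms are swapped. The same paragraph shows that its authors know how to ask for confidence limits, since they do so for recurrence, and no between-arm interval for fibrosis is named anywhere.

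The gap seems to matter most at grade 1. In Table 4, 68 of the 89 patients with fibrosis (76%) were grade 1, and the primary z-test leaves them out. If 8 Gy x 3 raised the rate of mild fibrosis and left grade 2-3 unchanged, non-inferiority could be declared and the only other planned result might be a non-significant chi-square. A reader could take that as evidence of no difference when a sizeable any-grade excess was still compatible with the data.

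**Working it through.** **1. The plan's own figures.** Inputs from section 13.0: 10% in both arms, margin 10 points, one-sided alpha 0.025, power 80%.

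n per arm = (1.960 + 0.842)² x 2 x 0.10 x 0.90 / 0.10² = 141.3, rounded up to **142**, as stated.

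Standard error at 142 per arm = √(0.18/142) = 0.0356. Final boundary = 0.10 - 1.97 x 0.0356 = **0.0299**, as in Table 7.

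None of these inputs involves the by-grade comparison, so an added interval would leave them as they are.

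**2. Grade 2-3.** The primary measure is already a difference in proportions. Comparing z with -1.97 against a 10-point margin is the same as asking whether the difference plus 1.97 standard errors lies at or below 0.10. At this cut-point an effect estimate is named and an upper confidence limit is built into the test.

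**3. Grade 1 and above, by example.** Table 4 scaled to 142 per arm gives expected counts at grades 0/1/2/3 of 96.2/35.0/9.3/1.5 (187, 68, 18 and 3, each times 142/276). Take an unfavourable illustration:

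| | Grade 0 | 1 | 2 | 3 | Any |
|---|---|---|---|---|---|
| 6 Gy x 5 | 96 | 35 | 9 | 2 | 46 |
| 8 Gy x 3 | 82 | 49 | 9 | 2 | 60 |

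Expected counts under no difference are 89, 42, 9 and 2 in each arm. Chi-square = 2 x 7²/89 + 2 x 7²/42 + 0 + 0 = 1.10 + 2.33 = 3.43 on 3 df, p = 0.33.

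The same planned table shows grade 1 at 35/142 = 24.6% against 49/142 = 34.5%, and any grade at 32.4% against 42.3%. Direction and size are visible without a further analysis.

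The precision follows from the two totals. The Wilson 95% limits are 25.2% to 40.5% for 46/142 and 34.4% to 50.5% for 60/142. Newcombe's method combines them:

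- difference = 0.4225 - 0.3239 = 0.0986
- lower limit = 0.0986 - √(0.0782² + 0.0807²) = -0.014
- upper limit = 0.0986 + √(0.0822² + 0.0715²) = 0.208

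The result is +9.9 points, 95% CI -1.4 to +20.8. It needs only counts that the comparison already requires.

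**4. Grade 3.** About 1.5 events per arm are expected. With 2 against 2 of 142 the Newcombe interval is ±3.7 points. An interval here would say little beyond the counts.

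**5. A side effect of adding intervals at every cut-point.** Suppose 13 of 142 patients on 6 Gy x 5 and 17 of 142 on 8 Gy x 3 have grade 2-3 fibrosis. The difference is 0.0282 and the unpooled standard error is √(0.1197 x 0.8803/142 + 0.0915 x 0.9085/142) = 0.0364. Then z = (0.0282 - 0.10)/0.0364 = -1.971, which meets the final boundary. The Newcombe upper limit for the same counts is 10.19 points, above the margin. A Newcombe interval at grade 2 or above could therefore appear to contradict the primary result that it is printed beside.

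**The case for a change.** The best argument for the concern is that the protocol itself shows interest in any-grade fibrosis: it quotes the 32% beside the 10%, and section 2.7 moves from the one-third figure straight to the non-inferiority design. A p-value of 0.33 beside a table does invite the reading that the arms are alike, and few readers will work out an interval themselves. Naming the cut-points and intervals in advance costs one sentence and removes any later choice.

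Part of this stands. The sentence indeed names no estimate, and an interval at grade 1 or above would help a reader. But the wording covers contingency table methods as well as chi-square tests and excludes no such interval. The obvious cut-point, any fibrosis, is already a total row in Table 4, so little is left to choose afterwards. Section 2.7 also gives a stated reason to put less weight on grade 1. Randomisation means that an excess there could still be informative, but the plan does not rest a conclusion on it.

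**Conclusion.** The concern does not hold. The plan compares proportions by grade and arm, and makes the grade 2-3 difference its primary measure with a test that carries its own confidence bound. Followed as written, it yields sound results. What is missing is a line of reporting detail, mainly the interval at grade 1 or above, which would be about ±10.8 points if 46 of 142 were seen in each arm. No figure, boundary or decision rule changes with or without it.

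This rests on three assumptions: the by-grade proportions are reported with their denominators, about 142 patients per arm are evaluable, and the z-test uses the unpooled variance, which reproduces both 142 per arm and the final boundary of 0.0299. The grade counts in the example are illustrative, with the 6 Gy x 5 arm set close to the Table 4 rates.

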Title	Prone partial breast irradiation (PBI): prospective randomized controlled non- inferiority trial to compare radiation fibrosis with five versus three fractions
Protocol Number	\$14-01306
Study Duration	5 years
Study Center (s)	Perlmutter Cancer Center
Study Hypothesis	A regimen of 8 Gy X 3 over 5 days (every other day) is as safe (well tolerated) and effective as 6 Gy X 5 over five consecutive days.
Objectives	 To prospectively randomize patients to one of two fractionation regimens of image –guided prone breast radiotherapy (PBI) as part of breast preservation in post-menopausal women with low risk-Tis or T1 breast cancers: 600cGy X 5 over five consecutive days (arm 1) versus 8 GyX3 given every other day (arm 2).
	2. To test the hypothesis that rate of post-treatment radiation fibrosis (grades 2+3) on the 8 Gy x3 arm is not more than 10% worse than the rate on 6 Gy x5.
	3. To estimate local control and evaluate cosmetic outcomes on the two arms.
Number of Subjects	Maximum number of patients to be enrolled 284.
Main Inclusion Criteria	 Post-menopausal women (50-90 years old) defined as either at least 2 years without menstrual period or patients at least 50 years or older with serological evidence of post-menopausal status or hysterectomized patients of any age with FSH confirmation of post-menopausal status. pT1 or low risk-pTis breast cancer, excised with negative margins. Criteria for low risk-pTis: Screen-detected Low to intermediate nuclear grade ≤ 2.5cm in size Resected with negative margins at ≥3mm)
Study Product, Dose Route, Regimen	Prone partial breast irradiation (PBI)
Statistical Methodology	Approximately 1 out of 10 patients experience grade 2-3 fibrosis after lumpectomy and partial breast radiation. Based on our prior experience, we observed a 10% rate of grade 2-3 fibrosis in these patients. With 142 patients randomized to each of the two treatment arms, we can test the hypothesis that the rate of fibrosis with 8Gy x3 is not more than 10% worse than the expected rate on the 6 Gy x 5 arm with one sided alpha =0.025 and power =80%.

TABLE OF CONTENTS

SCHEMA

1.0	OBJECTIVES	11
2.0	BACKGROUND AND HYPOTHESES	11
3.0	RESEARCH RISKS & BENEFITS	14
4.0	STAGING CRITERIA	18
5.0	RESEARCH POPULATION	18
6.0	REGISTRATION GUIDELINES	20
7.0	METHODS & PROCEDURES	22
8.0	RATIONALE FOR STUDY DESIGN	24
9.0	RADIATION THERAPY/TREATMENT PLAN	25
10.0	TOXICITIES TO BE MONITORED AND DOSAGE MODIFICATIONS	26

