2.3 Results of NYU 00-23: five year local control

The 5-year results of the initial clinical trial of prone PBI mentioned in 2.2 were recently reported (Formenti et al. *Int J Radiat Oncol Biol Phys. 2012 November 1; 84(3): 606-611. doi:10.1016/j.ijrobp.2012.01.039*). Post-menopausal patients with Stage I breast cancer with non palpable <2 cm tumors, negative margins, and negative nodes, positive hormonal receptors, and no extensive intraductal component (EIC) were eligible to NU 00-23. The trial was offered only once eligible patients had refused to undergo standard whole-breast radiotherapy. Patients were simulated and treated on a dedicated table for prone set-up. Radiation was delivered conformally, and was 30 Gy in five 6 Gy/daily fractions over 10 days with port film verification at each treatment. Recurrence in the ipsilateral breast, ipsilateral nodal, contralateral breast, and distant failure (IBF, INF, CBF, DF) were estimated using the cumulative incidence method. Disease-free, overall, and cancer-specific survival (DFS, OS, CSS) were recorded.

One hundred patients accrued to this IRB-approved prospective trial, one with bilateral breast cancer. One patient withdrew consent after simulation and another elected to interrupt radiotherapy after receiving two treatments. Ninety-eight patients are evaluable for toxicity and, in one case, both breasts were treated with PBI. Median patient age was 68 years (range 53-88 years); in 55% the tumor size was <1 cm. All patients had hormonal receptor positive cancers: 87% underwent adjuvant anti-hormonal therapy.

At a median follow-up of 64 months (range, 2-125 months), there was one local recurrence (1% in breast failure, IBF) and one contralateral breast cancer (1% contralateral breast failure,CBF). There were no deaths due to breast cancer by 5 year. Grade 3 late toxicities occurred in 2 patients (1 breast edema, 1 transient breast pain). Cosmesis was rated good/excellent in 89% of patients

with at least 36 months follow-up. The encouraging results of this trial have generated interest to further reduce the number of radiotherapy sessions for partial breast radiation, and compare five to three fractions, the purpose of this protocol.

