As shown in Table 2, the proposed hypo-fractionated schedule of 8Gy X 3 results in equivalent tumor control when compared with the standard regimen of six weeks of daily radiotherapy. In addition, as compared with the on-going NSABP trial (NSABP B-39 and RTOG 0413) and the NYU 6 Gy x 5 schedule, the proposed experimental schedule of 8 Gy x 3 fraction results in a lower calculated probability of acute effects and erythema, a similar probability for developing late radiation fibrosis as the NYU 6 Gy x 5 schedule and a slightly higher probability for developing late radiation fibrosis as compared to NSABP B-39/RTOG 0413. Specifically, we predict that the new 8 Gy X 3 schedule will result in comparable local control and toxicity of the previously tested 6GyX5 one, where the incidence of radiation fibrosis among 292 patients accrued ranged between 20-30%.

2.7 Risk of developing post-radiotherapy fibrosis: correlating a phenotype to a genotype – Genomic Analysis in order to determine genetic markers.

Exceeding a total dose of 60 Gy has shown to be associated with increased risk of fibrosis at the treated site. Even when the total dose is reduced, like in this trial (30 or 24Gy, respectively for arm 1 and 2), the use of fraction sizes in excess of the standard dose of 2 Gy may reflect in increased risk of fibrosis. This complication however occurs only in a minority of irradiated patients that currently cannot be identified in advance. While some induration at the original site is expected and it reflects the result of lumpectomy healing and seroma organization, fibrosis and retraction exceeding grade 1 (grade 2,3), is likely to represent a late effect of radiation.

Table 3 LENT SOMA DEFINITION OF FIBROSIS AND RETRACTION (appendix 2)

Objective Telangiectasia Fibrosis	<1 cm ² Barely palpable, increased density Asymptoteconstin	1-4 cm ² Definite increased intensity and firmness	>4 cm ² Very marked density, retraction, and fixation	
Edema Retraction, atrophy	Asymptomatic 10–25%	Symptomatic >25-40%	Secondary dysfunction >40-75%	
Ulcer	Epidermal only, <1 cm ²	Dermal only, >1 cm ²	Subcutaneous	

Not only does fibrosis compromise the cosmetic result but it also impairs the clinical exam of the breast. Post-radiation therapy fibrosis is characterized by mesenchymal cells replacing the normal tissue and overproducing extracellular matrix and it is clinically measured following the LENT/SOMA classification (Table 3 and appendix 2).

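### Do the unstated assessment time and grade rule for final fibrosis, and 284 evaluable out of a maximum 284 enrolled, undermine the primary analysis?

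*Combined protocol and SAP*

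**What the plan says.** The design paragraph of section 13.0 frames the hypothesis "with respect to the development of breast fibrosis". It sizes the trial at 142 per arm from a 10% rate of grade 2-3 fibrosis, a 10-point margin, one-sided alpha 0.025 and 80% power. The only time attached to a fibrosis assessment is in the interim rule: "The trial will have a planned interim analysis when 142 patients across both arms are evaluable for fibrosis assessment at 2 years from accrual".

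Both looks, at 142 and 284 patients, appear in Table 7 under one column headed "Number of Patients Randomized and Evaluable for Fibrosis". Its final boundary is z at or below -1.97, or a difference at or below 0.0299.

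The Analysis paragraph then states "The primary analysis will be the difference in proportions of patients with grade 2 or 3 fibrosis between the two treatment groups", tested by a non-inferiority z-test. Section 11.0 says fibrosis is graded by palpation using Appendix 2 (LENT/SOMA). The Study Summary sets the ceiling: "Maximum number of patients to be enrolled 284".

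**The concern.** Three things appear to be open in the final primary analysis.

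- **Time.** The Analysis paragraph gives recurrence at 1, 2 and 3 years but puts no time on fibrosis, and section 12.0 contains no fibrosis endpoint.
- **Grade rule.** Five post-treatment visits fall by 2 years (30 days, 90 days, 6 months, 1 year, 2 years). A patient with grade 2 at 1 year and grade 1 at 2 years is an event if the worst grade counts, and not if the 2-year grade counts. A patient with grade 2 at 1 year and no 2-year visit is an event on one rule and not evaluable on the other.
- **Evaluable number.** The final row of Table 7 needs 284 evaluable patients, which is also the enrolment maximum, so nothing is allowed for loss. Section 6.7 foresees withdrawal, and in the earlier trial of 100 patients (section 2.3) "Ninety-eight patients are evaluable for toxicity".

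A margin decided by a handful of patients could then depend on a rule chosen after the data were seen, and the stated 80% power would be optimistic.

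**Working it through.** **1. Reproduce the plan's figures.** Inputs from section 13.0: p = 0.10 in both arms, margin 0.10, one-sided alpha 0.025, power 80%.

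- n per arm = 2p(1-p)(1.960 + 0.842)² / 0.10² = 0.18 × 7.849 / 0.01 = 141.3, so 142 per arm and 284 in total, as stated.
- Final boundary: SE = √(0.18/142) = 0.0356, and 0.10 - 1.97 × 0.0356 = 0.0299, as stated.
- Interim boundary: SE = √(0.18/71) = 0.0504, and 0.10 - 2.96 × 0.0504 = -0.049 (stated -0.0493).
- With both looks, power is 80.0% and overall one-sided alpha 0.0249.

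So the design is correct for 284 evaluable patients, which is what the column heading says it counts.

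**2. Time.** The interim counts patients evaluable at 2 years. The final row has the same column heading and the same endpoint, with the number doubled. A group-sequential boundary presupposes the same endpoint at both looks, so 2 years is the reading that makes Table 7 coherent.

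**3. Grade rule.** Take 14 events of 142 (9.9%) on 6 Gy x 5, and use

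z = (p₂ - p₁ - 0.10) / √[p₁(1-p₁)/142 + p₂(1-p₂)/142], with boundary -1.97.

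| Events, 6 Gy x 5 v 8 Gy x 3 | z | Non-inferior? |
|---|---|---|
| 14 v 14 | -2.83 | yes |
| 14 v 17 | -2.13 | yes |
| 14 v 18 | -1.92 | no |
| 14 v 19 | -1.71 | no |
| 16 v 19 | -2.02 | yes |
| 19 v 19 | -2.48 | yes |

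Starting from 14 v 14, a change of grade rule reverses the result only if it adds a net 4 or more patients on 8 Gy x 3 and none on the control. Adding 5 to both arms, or 2 and 5, does not reverse it. Table 7's difference column would allow an excess of 4 (4/142 = 0.0282), but the z-test is the stated primary analysis, and here it allows 3.

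**4. Evaluable number.** Power = Φ(0.10/SE - 1.97), with SE = √(2p(1-p)/n). The loss rates are assumed, since the documents give none. The second rate is Table 4's 21/276 = 7.6%.

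| Not evaluable (assumed) | n per arm | Power at 10% | Power at 7.6% |
|---|---|---|---|
| 0% | 142 | 80% | 89% |
| 2% | 139 | 79% | 88% |
| 10% | 128 | 76% | 85% |

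At 7.6%, 112 per arm still gives 80%, so 142 - 112 = 30 per arm could be lost. With 10% loss the two-look alpha is 0.0248, so the type I error is not inflated.

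**The case for a change.** The strongest case for amending is that the gap is real and cheap to close. Nothing in the documents chooses between the grade at the visit and the worst grade to date, and nothing defines evaluable. The hypothesis wording leans towards ever developing fibrosis, while the interim wording leans towards a visit. The planning rate was measured after a minimum of 6 months, which is a third time frame. Grading is by palpation, and section 2.7 says "While some induration at the original site is expected and it reflects the result of lumpectomy healing and seroma organization", so a one-grade change between visits is plausible. Table 4 implies about 68/276 × 142 = 35 grade 1 patients per arm who could cross the threshold.

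What stands is the silence; a clarifying sentence would be harmless. The rest weakens on reading:

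- The two phrases in section 13.0 are a general statement of the hypothesis and a trigger for the interim look. Neither is a grading rule, so they do not conflict.
- The same sentence of section 2.7 goes on to treat fibrosis above grade 1 as a probable late radiation effect. That separates healing from the grade 2-3 endpoint.
- Of the five visits, only three (6 months, 1 year, 2 years) fall in the period over which the planning rate was measured.
- The documents give no reason to expect grades to regress more in one arm. Table 2 models the same fibrosis effect in both, 120 Gy₂.

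The evidence on loss is also thin. In the earlier trial, one patient withdrew after simulation and one stopped radiotherapy after two treatments; neither is described as missing a late visit. Section 2.5 refers to "the incidence of radiation fibrosis among 292 patients accrued" and Table 4 to 276, but no reason is given for the difference, so it cannot serve as a loss rate.

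**Conclusion.** No change to the plan is needed. Two years is the coherent reading for both looks. The remaining choice, visit grade or worst grade, is missing detail that analysts can settle sensibly, with the alternative available as a sensitivity analysis. Reversing a 14 v 14 result would take a net 4 or more patients reclassified in one arm only, and the documents do not point to that.

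The 80% power is correct as written for 284 evaluable patients. Assumed losses of 2% to 10% cost about 1 to 4 points at the 10% planning rate and leave 88% to 85% at Table 4's 7.6%. Enrolling more patients to recover that is a design preference and does not correct an error.

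This rests on three assumptions: the arms truly have equal rates, loss is similar in the two arms, and the control rate is near 7.6% to 10%. A higher control rate would lower power (65% at an assumed 15% with all 284 evaluable), but that comes from the planning rate and not from the points raised here.
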